- D. Unscheduled clinic visits are to be conducted in all cases of suspected symptomatic and asymptomatic VTE, progression/recurrence of VTE, paradoxical embolism (PDE), occurrence of post-thrombotic syndrome (PTS), major or clinically relevant bleeding events (MBEs / CRBEs) or other suspected significant AE or SAE. The unscheduled visit should be performed as soon as possible, preferably within 24 hours after the site first becomes aware of a suspected event. This visit should include all appropriate diagnostic procedures. If VTE progression/recurrence, PDE, PTS, MBEs, CRBEs are confirmed, the patient taking dabigatran etexilate is to be discontinued from the dabigatran etexilate treatment arm (eEOT visit to be performed as soon as possible), and an appropriate standard of care VTE treatment should be initiated per the investigator's discretion and/or local guidelines and the patient should be followed for the remainder of the study. If it is decided that a patient is to be discontinued from treatment due to an event, an eEOT visit should be conducted.
An unscheduled Visit is also to be performed in case a dabigatran etexilate dose adjustment is needed.
- E. The early End Of Treatment (eEOT) visit will be required for all patients who have taken a dose of dabigatran etexilate but failed to complete the full planned treatment observation period (completion of Visit 8). If feasible, this visit is also required for patients randomized to SOC should they decide to discontinue the trial or permanently stop SOC treatment for any reason. eEOT visit is not required if the SOC treatment is changed during the course of the trial.
- F. The informed consent (and if applicable assent) should be obtained per local legislations and guidelines from the patient's parent(s) or legal guardian and patient where applicable before any study procedures are performed. Should patients reach legal age during the trial they must personally sign and date the informed consent form as soon as possible and, at the latest, at the next visit
- G. Prior to start of therapy, all study inclusion and exclusion criteria must be checked to confirm patient eligibility.

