5. VARIABLES AND THEIR ASSESSMENT

5.1 EFFICACY - PHARMACODYNAMICS

5.1.1 Endpoints of efficacy

Primary endpoint:

Efficacy combined endpoint Proportion of patients with:

- Complete thrombus resolution and;
- Freedom from recurrent VTE (including symptomatic and asymptomatic, contiguous progression or non-contiguous new thrombus, deep vein thrombosis, pulmonary and paradoxical embolism, thrombus progression) and;
- Freedom from mortality related to VTE.

The events outlined in the above combined primary endpoint will be assessed by radiologists or other such qualified clinicians using an appropriate method such as ultrasound, echocardiography, venography or computed tomography (CT scan) based on the location of the thrombus and the test used to perform the baseline assessment.

All components of the primary efficacy endpoint as well as all bleeding and all fatal events will be centrally adjudicated by an independent blinded committee.

Secondary endpoints:

- Freedom from major bleeding events (MBEs), defined as either fatal bleeding; clinically overt bleeding associated with a decrease in haemoglobin of at least 20 g/L in a 24-hour period; bleeding that is retroperitoneal, pulmonary, intracranial or otherwise involves the central nervous system; or bleeding that requires intervention in an operating suite.
- Pharmacokinetic and pharmacodynamic assessments at visit 3 (after at least six consecutive dabigatran doses) and after at least 3 days following any dabigatran dose adjustment
- Frequency of dose adjustments (i.e. Number of subjects with dose adjustment), temporary and permanent discontinuation from therapy and number of subjects with laboratory monitoring requirements for dose adjustment during the treatment phase
- Frequency of switch of type of anti-coagulation therapy (including dabigatran to SOC) (Frequency of subjects switching the type of anti-coagulation therapy including dabigatran etexilate to standard of care and switching from an intended standard of care treatment to another)
- Freedom from thrombus progression at end of therapy (day 84 after randomisation (Visit 8) or eEOT whichever comes first) compared to baseline
- Assessment of the acceptability of an age-appropriate formulation at end of therapy
- All bleeding events

Proprietary confidential information.

© 2019 Boehringer Ingelheim International GmbH or one or more of its affiliated companies. All rights reserved.

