7.3.2 Secondary analyses

Secondary analyses of primary endpoint

Proprietary confidential information.

© 2019 Boehringer Ingelheim International GmbH or one or more of its affiliated companies. All rights reserved.

This document may not - in full or in part - be passed on, reproduced, published or otherwise used without prior written permission.

Secondary analysis of the proportion of patients with complete thrombus resolution, with no recurrent VTE and no VTE-related death will consider age group as covariate and the treatment and age group interaction in a logistic regression model using ITT as the primary analysis.

Analyses of secondary endpoints

Major bleeding events will be analysed as time-to-event endpoint using Kaplan-Meier method. The proportion of patients free from major bleeding events at the end of planned treatment period (84 days (Visit 8) or eEOT) will be provided by Kaplan-Meier estimates for the two treatment arms pooling all age groups. Due to the low event rate of major bleeding, age group stratification will not be considered in the primary model for this endpoint. The confidence interval of proportion difference will be calculated based on Kaplan-Meier estimates and its variances. This safety analysis will be based on the treated set which will include events that occur between the date of first dose of study medication to the date of last dose of medication plus six-days (on treatment analysis). Patients who do not have major bleeding events during the treatment period and patients who discontinue from the trial prematurely without having major bleeding events will be censored. For patients who have more than one event during the trial, the time to the first occurrence of the event will be considered for the analysis.

Pharmacokinetic and pharmacodynamic analyses will be summarized in [Section 7.3.5](#) and [Section 7.3.6](#).

Frequency of dose adjustments, temporary and permanent discontinuation from therapy, number of laboratory monitoring requirements for dose adjustment during the treatment phase and frequency of switch of type of anti-coagulation therapy (including dabigatran to SOC) will be summarized descriptively for each treatment arm.

Freedom from thrombus progression at baseline will be summarized descriptively and for each treatment arm. Frequency of patients free from thrombus progression at day 84 after randomization (or eEOT, whichever comes first) will be analysed descriptively.

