5. ENDPOINTS

5.1 PRIMARY ENDPOINT

The efficacy combined endpoint is the proportion of patients with:

- Complete thrombus resolution and;
- Freedom from recurrent venous thromboembolism (VTE, including symptomatic and asymptomatic, contiguous progression or non-contiguous new thrombus, deep vein thrombosis, pulmonary and paradoxical embolism, thrombus progression) and;
- Freedom from mortality related to VTE.

All components of the primary efficacy endpoint will be centrally adjudicated by an independent blinded committee.

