7.4 PRIMARY ENDPOINTS

Primary analysis

The primary analysis of the primary efficacy endpoint will be performed on the randomized set following the intention-to-treat (ITT) principle, based on adjudicated data. For example: patients who were originally randomized to DE and later switched to SOC before Day 84, as cases of premature termination of the study medication, will be further followed up per the visit schedule until Day 84.

The analysis period in the primary analysis starts from the time of randomization to the time point of interest, that is, Day 84 \pm 7 days.

- For patients who die or withdraw consent prior to Day 84 – 7 days, the period for the primary analysis ends with the date of trial completion (i.e. the date of death, or the date of consent withdrawal).
- For patients who discontinue treatment prematurely (for example, due to complete thrombus resolution, AE, DE concentration out of target range after one dose modification, and so on), the latest available thrombus assessment up to Day 84 + 7 days will be used for the primary analysis. In particular, thrombus assessment performed after eEOT but before/at Visit 8 for patients switching from DE to SOC will be used for primary analysis. In terms of the recurrent VTE component or VTE-related mortality component, recurrence or death up to Day 84 + 7 days will be used for primary analysis.
- Patients who are still being treated and have not yet reached Day 84 \pm 7 days at time of EMA interim data cut-off will not be included in the analysis

The primary efficacy endpoint contains three components. Given the composite nature of the primary endpoint, each component will be evaluated separately, and a joint outcome of achieving the primary endpoint will be concluded only if all three components are satisfied.

Component 1: free from VTE-related mortality

Patients with VTE-related death occurring between randomization to Day 84 + 7 days will be considered as NOT meeting the endpoint in terms of the component of “freedom from mortality related to VTE”, and therefore will not contribute to the proportion of patients achieving the primary efficacy endpoint.

Component 2: free from recurrent VTE

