Permanent discontinuation from therapy and the reasons will be summarized in the disposition table.

Assessment of acceptability

Assessment of acceptability of an age-appropriate formulation at the end of therapy will be provided descriptively for DE treated patients.

Assessment of acceptability of capsules, pellets and OLF reconstituted with flavoured or unflavoured solvent at Days 3 (Visit 3), 21 (Visit 5) and 84 (Visit 8), or eEOT after randomisation will be summarized descriptively as well. Questions completed by investigator, by parent/legal guardian, and by patients (if old enough per investigator judgement) will be summarized descriptively.

Thrombus progression

Frequency of patients free from thrombus progression at day 84 ± 7 days after randomization (or eEOT, whichever comes first) will be analyzed descriptively by treatment arm and age group. Patients without VTE assessments by this time point will be summarized as well. Mortality related to VTE will be considered as recurrence of VTE.

All bleeding events and all-cause mortality

All adjudicated bleeding events and adjudicated all-cause mortality will be analyzed as time-to-event endpoint using stratified Cox proportional hazard model with treatment as a covariate in the model and age group as the stratification factor. A pooling of age groups might be necessary if no events were observed in certain age group.

Patients that do not experience any bleeding events will be included as censored observations at the date of patients' last visit, the date of death not related to bleeding, or the date of data cut-off, whichever comes first. Patients being alive at the end of observational period will be censored for all-cause mortality at the date of patients' last date known to be alive, or the date of data cut-off whichever comes first. All bleeding events and all-cause mortality based on treated set will be analysed descriptively and by Kaplan-Meier estimates for each treatment arm.

Incidence of bleeding events including MBEs, CRNM, minor bleeding events, and any bleeding events will be presented, as well as incidence of combined endpoint of major and CRNM bleeding events.

Components of efficacy endpoint

All components of the primary endpoint will be analyzed as proportions using adjudicated data as the primary analysis in [Section 7.4](#). Concordance between adjudicated events and investigator-reported events will also be summarized.

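### Freedom from thrombus progression is read at eEOT after a dabigatran-to-SOC switch but at Day 84 after a change of SOC drug, so the arms are not compared like for like; the direction of bias is undetermined and the effect small

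*SAP*

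**What the plan says.** Protocol 5.1.1 defines this secondary endpoint at end of therapy, that is, Day 84 "or eEOT whichever comes first) compared to baseline". Protocol 7.3.2 gives the analysis: "Frequency of patients free from thrombus progression at day 84 after randomization (or eEOT, whichever comes first) will be analysed descriptively". SAP 5.2.2 repeats the definition. SAP 7.5.2 adds a window and tabulates by arm and age group the children "free from thrombus progression at day 84 ± 7 days after randomization (or eEOT, whichever comes first").

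Whether an eEOT takes place depends on the arm. Footnote E of the protocol Flow Chart states: "The early End Of Treatment (eEOT) visit will be required for all patients who have taken a dose of dabigatran etexilate" and did not complete Visit 8. For the comparator it states: "eEOT visit is not required if the SOC treatment is changed during the course of the trial". A SOC child who stops altogether is treated differently: "If feasible, this visit is also required for patients randomized to SOC should they decide to discontinue the trial or permanently stop SOC". Protocol 6.2.3 agrees: a move from dabigatran to SOC is an early discontinuation, and a move between SOC drugs is not.

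The primary analysis follows another rule. Under SAP 7.4, for a child who discontinues early, "the latest available thrombus assessment up to Day 84 + 7 days will be used for the primary analysis", and recurrence counts up to the same day. Recurrent VTE, as defined in SAP 5.1, includes "contiguous progression or non-contiguous new thrombus, deep vein thrombosis, pulmonary and paradoxical embolism, thrombus progression".

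The analysis sets also differ. Protocol Table 7.3.1: 1 lists secondary efficacy endpoints under intent-to-treat on the randomised set, whereas SAP 6.3 places this one on the treated set.

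**The concern.** The reading time depends on something that happens after randomisation, and a change of anticoagulant triggers it for dabigatran but not for SOC. The dabigatran arm also has a reason to stop that SOC lacks: a trough concentration still out of range after one adjustment (protocol 3.3.4.1, 4.1.3). Protocol 2.3 puts the first adjustment at about 5 to 12 days after first intake, and 4.1.3 repeats the sample about 3 days later, so an eEOT can come within the first weeks.

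Two things are at stake. A table by arm would compare children observed for different lengths of time. And one child could be counted in opposite ways: a recurrence in the primary component, yet free from thrombus progression in the secondary endpoint of that name.

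**Working it through.** **Inputs**
- Arm sizes: 94 dabigatran, 47 SOC (protocol 7.6).
- Share stopping dabigatran early, s: up to 15% (protocol 7.6, covering this trial and 1160.108).
- 84-day progression risk, r: not given. Proxies are the 5.6% and 10.0% with recurrent VTE or death in the two arms of the randomised paediatric heparin trial described in protocol 1.1. I add 3% as a lower assumption.
- Switch day, t: not given; Day 10 and Day 42 assumed.
- Timing of risk: uniform, or front-loaded, because protocol 2.3 says recurrence risk is highest in the first 30 days.

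**The plan's own figure.** No figure is stated for thrombus progression. The calculation that uses the 15% reproduces: 120 − 0.20 × 94 = 101.2, taken as 101; 94 + 101 = 195; 195 × 0.85 = 165.75, stated as 166. In this trial 15% is 0.15 × 94 = 14.1 children.

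**Event reading (no progression up to the time point).** Hidden dabigatran progression = s × r × (1 − F(t)), where F(t) is the share of the 84-day risk already past at the switch.
- Uniform: F(t) = t/84.
- Front-loaded: F(t) = (1 − e^(−kt)) / (1 − e^(−84k)) with k = ln 4/30. This puts about 77% of the risk in the first 30 days and gives F(10) = 0.378 and F(42) = 0.874.

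Percentage points hidden at s = 15% (children of 94 in brackets):

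| Risk shape | Switch day | r = 3% | r = 5.6% | r = 10% |
|---|---|---|---|---|
| Uniform | 10 | 0.40 (0.37) | 0.74 (0.70) | 1.32 (1.24) |
| Uniform | 42 | 0.22 (0.21) | 0.42 (0.39) | 0.75 (0.70) |
| Front-loaded | 10 | 0.28 (0.26) | 0.52 (0.49) | 0.93 (0.88) |
| Front-loaded | 42 | 0.06 (0.05) | 0.11 (0.10) | 0.19 (0.18) |

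For example, 0.15 × 0.10 × (1 − 10/84) = 0.0132, and 0.0132 × 94 = 1.24. Doubling s to 30% raises the maximum to 2.64 points (2.48 children).

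**Status reading (worse than baseline at the time point or not).** Take equal true risk r in both arms. A dabigatran child whose VTE worsens comes off dabigatran (Flow Chart footnote J) and is read at eEOT while worse. A SOC child with the same event who changes SOC drug is read at Day 84. Let q be the share of SOC progressions no longer worse than baseline by then. Observed progression is r − s × r × (1 − F) on dabigatran and r × (1 − q) on SOC, so:

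freedom, dabigatran minus SOC = r × [s × (1 − F) − q].

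With r = 5.6%, s = 15%, uniform risk and a Day 42 switch, s × (1 − F) = 0.075:
- q = 0: 0.056 × 0.075 = +0.4 points
- q = 25%: 0.056 × (0.075 − 0.25) = −1.0 points
- q = 50%: 0.056 × (0.075 − 0.50) = −2.4 points

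The sign turns at q = 7.5%. For a Day 10 switch under uniform risk it turns at 0.15 × 74/84 = 13.2%. For a Day 42 switch under front-loaded risk it turns at 0.15 × 0.126 = 1.9%. The documents give no value for q.

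**One child, two results.** Suppose a child leaves dabigatran on Day 20 and progresses on Day 60. Day 60 is before Day 91, so SAP 7.4 counts a recurrence and the child fails the primary endpoint. SAP 7.5.2 reads the same child at eEOT, around Day 20, as free from progression.

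**After the fix.** If events count to Day 84 + 7 in every child, the truncation term is zero in both arms, provided the planned follow-up takes place.

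**The case against.** The best defence is that this is an end-of-therapy endpoint by design. The wording is consistent across both documents. The SAP puts the endpoint on the treated set, whose window in protocol 7.3 closes six days after the last dose when treatment stops early. In the Day 20/Day 60 example the child progresses on SOC, 40 days after leaving dabigatran, so an on-treatment reading properly leaves that event out. The event is not lost either, because the recurrent VTE component catches it on adjudicated data in the randomised set and is reported separately. Nothing is tested on this endpoint, and no key secondary endpoint is defined.

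Much of that stands, and it limits how far the point reaches. It does not make the table like for like. Protocol Table 7.3.1: 1 lists secondary efficacy endpoints as intent-to-treat, and nothing in SAP 7.5.2 labels this one on-treatment or warns that the arms are read at different times.

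Two further limits also stand. A reader might infer that observation is cut short in the dabigatran arm only. Footnote E does not support this: SOC children who stop for good have an eEOT where feasible, and protocol 3.3.4.1 does not confine the early stop for complete resolution to dabigatran. Follow-up also continues after eEOT. Second, the 15% is an upper figure, covers two trials and includes stops that would produce an eEOT under SOC too, so it is not the gap between the arms.

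**Conclusion.** The point holds in a limited form. Among children who change anticoagulant, the endpoint is read at different times in the two arms, and it can contradict the primary component for the same child.

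A reader might go further and infer that the comparison favours dabigatran. The documents do not support that, because they do not say whether the endpoint is an event up to the time point or a status at it. The comparison with baseline at end of therapy suggests status. The sentence in SAP 7.5.2 that treats VTE-related death as a recurrence leans towards an event. Under the event reading truncation can only favour dabigatran; under the status reading the sign can reverse.

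Under the event reading the size is about 0.1 to 1.3 percentage points, roughly one dabigatran child or fewer, at 15% early stops. Under the status reading it depends on the unknown regression share: +0.4 to −2.4 points in the case worked above. Progression risk, switch day, timing of risk and regression share are all assumptions. The primary analysis is unaffected, so this is a correction to a descriptive secondary table.

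**What to change.** In SAP 7.5.2, with 5.2.2 aligned:
- State that the endpoint counts any adjudicated thrombus progression from randomisation to Day 84 + 7. This is an event definition, not status at the latest image; the two classify a child who progresses and then regresses differently, so only one should be used.
- Summarise it by arm for all randomised children regardless of treatment switch, in line with protocol Table 7.3.1: 1 and the primary-analysis window.
- Keep the reading at the earlier of Day 84 and eEOT as a summary on the treated set, labelled on-treatment. The protocol-defined result is then still reported.
- Record the change in SAP section 4, since protocol 5.1.1 and 7.3.2 carry the end-of-therapy wording.

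No new assessments are needed. Flow Chart footnote J asks early-discontinued children to complete at least Visits 8 and 9, where feasible. SAP 7.4 schedules the index thrombus assessment at Day 84 ± 7 whatever the treatment status, and progression is already adjudicated as part of recurrent VTE. The cost is the SAP wording and one extra table, some overlap with the recurrent VTE component, and a dabigatran figure that may look slightly less favourable.

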7.7 EXTENT OF EXPOSURE

Only descriptive statistics are planned for this section of the report. Summaries will be provided for treated set. Total exposure (in days) is defined as date of last administration of DE/SOC – date of first administration of DE /SOC + 1, ignoring the temporary interruptions, i.e. intermittent off-treatment periods were considered in the extent of exposure.

For DE treated patients, listings on exposure, including the actual treatment received, starting dose, formulation type, dates of first and last doses, the total treatment time, whether a dose adjustment was done, whether patient switched to SOC, and reason for change will be provided.

For SOC treated patients, listings on exposure, including the SOC treatment type, medication name, dates of first and last doses, the total treatment time, whether a SOC change was done, and reason for change will be provided.

Dose adjustment, interruption and discontinuation are analysed as secondary endpoints and specified in [Section 7.5](#).

The number and percentage of patients with DE trough plasma concentrations in the target range (50 to < 250 ng/mL) and outside target range while on treatment will be presented.

7.8 SAFETY ANALYSIS

The analysis for MBEs is detailed in [Section 7.5](#).

All safety analyses will be performed on treated set during on-treatment period.

7.8.1 Adverse events

The analyses of AEs will be descriptive in nature and will be based on BI standards as presented in the corporate guideline: “Analysis and Presentation of Adverse Event Data from Clinical Trials” [001-MCG-156] [\(4\)](#).

AEs will be coded with the most recent available version of MedDRA referred to in the footnote of tables and listings.

All analyses of AEs will be based on the number of patients with AEs (and not on the number of AEs). For this purpose, AE data will be combined in a 2-step procedure into AEs records.

In a first step, AE occurrences, i.e. AE entries on the electronic case report form (eCRF), will be collapsed into AE episodes provided that all of the following applies:

- The same lowest level term was reported for the occurrences;
- Occurrences were time-overlapping or time-adjacent (the second occurrence started at the end date of first occurrence);
- Treatment did not change between the onset of occurrences or treatment changed between the onset of occurrences, but no deterioration was observed for the later occurrence.

In a second step, AE episodes will be condensed into AE records provided that episodes are reported with the same term on the respective MedDRA level and that the episodes are assigned to the same treatment.

The analysis of AEs will be based on the concept of treatment emergent AEs. All AEs occurring before drug intake will be assigned to ‘screening’. For DE patients not switching to SOC, all AEs recorded between first DE intake until 6 days after the last administration of DE will be assigned to DE on-treatment period. AEs with onset date after that period will be assigned to post-treatment period. For DE patients who switched to SOC, AEs occurred after patients’ last administration of DE plus 6 days and before 6 days after last administration of SOC will be assigned to SOC on-treatment period. For patients in SOC arm, all AEs occurred between the first drug intake of SOC until 6 days after the last administration of any SOC will be assigned to the on-treatment period (regardless of switching between types of SOC treatment). In addition, AEs occurring before first drug intake but worsening in intensity during the treatment period will also be assigned to the administrated treatment. For details on the treatment definition, see [Section 6.1](#).

All AEs (including bleeding) in the on-treatment period will be tabulated. AEs occurring outside the on-treatment period will be summarized in listings only and assigned to ‘screening’, ‘post-treatment’, or ‘post-study’.

According to ICH E3 (5), AEs classified as ‘other significant’ will include those non-serious and non-significant AEs with

- (i) ‘action taken = discontinued’ or ‘action taken = reduced’, or
- (ii) marked haematological and other lab abnormalities or lead to significant concomitant therapy as identified by the Clinical Trial Leader/Investigator at a Medical Quality Review Meeting.

An overall summary of AEs will be presented.

Frequency of patients with AEs will be summarised by age group, treatment, primary system organ class and preferred term. Separate tables will be provided for patients with other significant AEs according to ICH E3 (5), for patients with serious adverse events (SAEs), protocol-specified adverse events of special interest (AESIs), for patients with drug related AEs, as well as patients with AEs leading to treatment discontinuation and death. The system organ classes and preferred terms will be sorted by descending order of frequency.

The following are considered as protocol-specified AESI:

- Hepatic injury defined by the following alterations of liver parameters: An elevation of AST and/or ALT ≥ 3 fold ULN combined with an elevation of total bilirubin ≥ 2 fold ULN measured in the same blood draw sample.
- Creatinine value shows a ≥ 2 fold increase from baseline and is above the upper limit of normal.

